### **8.2.2. Inclusion Criteria**

Patients must meet all of the following inclusion criteria to be eligible for inclusion in the study:

- Men and women aged  $\geq 18$  years;
- Cardiology patients# who has been prescribed atorvastatin by physician's clinical judgment under normal clinical care. These patients will include those with established coronary heart disease, or having multiple risk factors and at risk for cardiovascular disease, or primary hypercholesterolemia.
- Baseline laboratory reports\* prior to starting atorvastatin therapy can be tracked, including lipid measurement, liver function, creatine kinase (CK) value, and renal function.
- Evidence of a personally or his/her legally acceptable representative signed and dated informed consent document indicating that the patient has been informed of all pertinent aspects of the study and accept follow-up visit.

#The proportion of ward inpatients is not more than 20% of the total number of patients.

\*The date of the report should be within 1 month before taking atorvastatin or within 24h after starting atorvastatin therapy.

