#### 8.2.4. Disease Diagnostic Basis

Refer to local clinical diagnosis and treatment guidelines listed below:

- Refer to chronic stable angina pectoris diagnosis and treatment guideline issued by Chinese Medical Association in 2007, Non-ST-segment elevation acute coronary syndrome diagnosis and treatment guideline issued by Chinese Medical Association in 2012, ST-segment elevation acute myocardial infarction diagnosis and treatment guideline issued by Chinese Medical Association in 2015, respectively to diagnose coronary heart disease
- Refer to Chinese Hypertension Prevention Guideline 2010 to diagnose hypertension.
- Refer to Chinese Guideline on Dyslipidemia Prevention and Treatment in Adult 2007 to diagnose hyperlipidemia.

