#### 8.2.5. Risk Stratification and LDL-C Therapy Target Value

Referring to Chinese Guideline on Dyslipidemia Prevention and Treatment in Adult (2007), the cardiovascular disease (CVD) risk stratification and LDL-C therapy target value will be the following:

Risk stratification	Beginning of drug therapy	Therapy target value
Low-risk: 10 years CV risk <5%	LDL-C $\geq$ 4.92mmol/L (190mg/dl)	LDL-C<4.14 mmol/L (160mg/dl)
Medium-risk: 10 years CVD risk 5%~10%	LDL-C $\geq$ 4.14 mmol/L (160mg/dl)	LDL-C<3.37 mmol/L (130mg/dl)
High risk: CHD or CHD risk equivalents, or 10 years CV risk 10%~15%	LDL-C $\geq$ 2.59 mmol/L (100mg/dl)	LDL-C<2.59mmol/L (100mg/dl)
Very high risk: acute coronary syndromes, or ischemic cardiovascular disease combined with diabetes	LDL-C $\geq$ 2.07 mmol/L (80mg/dl)	LDL-C<2.07mmol/L (80mg/dl)

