6.2 SECONDARY ENDPOINTS

- Lipid parameters (LDL-C, *High-Density Lipoprotein Cholesterol* (HDL-C), Total Cholesterol (TC), and Triglycerides (TG)) at week 12, change from baseline in lipid parameters, and %change from baseline in lipid parameters at week 12, overall, and by CVD risk group.
- *Dosage distribution of atorvastatin in patients by CV risk stratification at the end of 12-week follow-up defined as follows:*

- The atorvastatin total dose in each patient will be calculated from Day 1 to Week 12/or last dose day.
- The patient daily dose will be the total dose divided by the total days of receiving atorvastatin.
- The Week 12 dose will be the dose taken at Week 12.

- **Duration on Study**

Duration on treatment group for each subject will be calculated as last treatment day – first dose date +1

- **Adverse Events**

Any new findings or worsening of findings at post-baseline visits will be reported as adverse events.

An adverse event is considered treatment emergent relative to a given treatment if:

- the event occurs for the first time during the effective duration of treatment and was not seen prior to the start of treatment, or
- the event was seen prior to the start of treatment but increased in severity during treatment.

- **Adverse Events Special Interest (AESI)**

The Adverse Events Special Interest (AESI) will be categorized as below:

- Muscle symptoms: myalgia, fatigue, weakness, creatine kinase values 10 times the upper limit of normal, or rhabdomyolysis, and muscle damage based on significant elevated creatine kinase (CK)
- Major cardiovascular events: myocardial infarction, stroke, unstable angina requiring re-hospitalization, revascularization with either percutaneous coronary intervention or coronary-artery bypass grafting
- Death

- **Abnormal Laboratory Data**

The following elevated abnormal laboratory data will be summarized.

- Significant elevated CK: CK values 10 times the upper limit of normal,
-
-

- Persistent elevation in alanine aminotransferase, aspartate aminotransferase, or both: two consecutive measurements obtained 4 to 10 days apart that is more than three times the upper limit of the normal range
- **Dropout**
Dropout percentages and reason through 12 weeks of follow-up

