Percentage of patients who drop out of the study and reasons for discontinuation will be summarized overall and by dose group within each CVD risk level.

Laboratory Data

The percentage of patients with abnormal laboratory values will be summarized overall and by dose group within each CVD risk level for CK, Aspartate Aminotransferase (AST), and Alanine Aminotransferase (ALT).

Descriptive summary will be provided for change from baseline for clinical laboratory by overall and dose group within each CVD risk level.

The baseline is the last non-missing value prior to treatment start.

Prior and Concomitant Medications

Prior and concomitant medications will be coded by WHO medical dictionary; patients who received these medications will be listed and summarized overall, and by dose group within each CVD risk level.

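### The muscle-event count and the mean CK/AST change do not separate infarct-related values, although acute coronary patients are eligible

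*SAP*

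**What the plan says.** **Muscle category.** SAP 6.2 defines it as "Muscle symptoms: myalgia, fatigue, weakness, creatine kinase values 10 times the upper limit of normal, or rhabdomyolysis", and adds "muscle damage based on significant elevated creatine kinase (CK"). The laboratory list in the same section gives the threshold: "Significant elevated CK: CK values 10 times the upper limit of normal". No symptom, timing or cardiac-source condition is attached. Protocol 8.1.2 also lists CK at 10 times ULN among the muscle events, so the criterion itself comes from the protocol.

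**Cardiovascular category.** The next item in SAP 6.2 is "Major cardiovascular events: myocardial infarction, stroke, unstable angina requiring re-hospitalization, revascularization with either percutaneous coronary intervention or coronary-artery bypass grafting". No rule links the two categories.

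**Laboratory change.** SAP 8.2 states: "Descriptive summary will be provided for change from baseline for clinical laboratory by overall and dose group within each CVD risk level". Baseline is the last available value before treatment starts.

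**Who is eligible.** Protocol 8.2.4 relies, among other sources, on the "ST-segment elevation acute myocardial infarction diagnosis and treatment guideline issued by Chinese Medical Association in 2015" to diagnose coronary disease, and also on a non-ST-elevation ACS guideline. Protocol 8.2.5 defines the top stratum as "Very high risk: acute coronary syndromes, or ischemic cardiovascular disease combined with diabetes". Protocol 8.2.3 has two exclusions, and neither mentions recent MI. Ward inpatients are allowed up to a limit: "The proportion of ward inpatients is not more than 20% of the total number of patients".

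**What is measured.** Protocol 8.3 lists CK, ALT, AST and bilirubin. It lists no cardiac-specific marker.

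**The concern.** Infarcted heart muscle releases CK and AST. This is general clinical knowledge and is not stated in the documents. In this cohort it can act in two ways, and they run in opposite directions.

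- **An MI or revascularization during follow-up.** A CK of 10 times ULN recorded around the event counts as a muscle event, and the event itself counts as a cardiovascular one. The muscle count goes up for a cardiac reason.
- **An infarct at baseline.** If atorvastatin is started during an acute MI, the last pre-treatment CK and AST may be infarct values that have returned to normal by Week 12. That fall enters the change-from-baseline mean as a decrease over the treatment period.

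The muscle count could therefore look too high while the mean CK change looks too favourable. A reader of the final tables would have no means of telling how much of either is cardiac. Protocol section 6 gives the safety of high-intensity statin in Chinese patients as part of the rationale, and these summaries are reported by dose, so the ambiguity falls on a question the study wants to inform.

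**Working it through.** **The plan's own figure.** The documents give no expected rate or distribution for CK, AST or MI. Their only computed figure is the sample size: 1.96² × 0.60 × 0.40 / 0.011² ≈ 7,620, against 7,600 stated, and 7,600 / (1 − 0.24) = 10,000. It reproduces, but it bears on this point only as the denominator used below.

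**Do existing rules separate cardiac from skeletal CK?**

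- *Investigator causality* (protocol section 10) feeds a table of treatment-related events. The special-interest table in SAP 8.2 is not limited to related events.
- *The treatment-emergent rule* (SAP 6.2) deals with a CK already raised at baseline, unless it worsens. It does not deal with a new MI on treatment, and it is not said to govern the laboratory percentages.
- *Unscheduled results* (SAP 8.1) are mainly only listed, but those that qualify for a derived endpoint are excepted.
- *Risk-level tables* put all ACS patients in the very-high stratum, where they are mixed with ischemic cardiovascular disease plus diabetes. The overall row pools everyone.

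Each is partial, and none identifies the source of a CK value.

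**Double counting (all rates assumed).** Cardiac-source CK cases = N × MI rate × share of MIs with a recorded CK of at least 10 × ULN. Other cases = N × true rate. N = 10,000.

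| Assumed true rate | Assumed MI rate | Assumed share recorded | Other cases | Cardiac cases | Cardiac share |
|---|---|---|---|---|---|
| 0.1% | 0.2% | 10% | 10 | 2 | 2/12 = 17% |
| 0.05% | 0.5% | 30% | 5 | 15 | 15/20 = 75% |
| 0.01% | 1.0% | 50% | 1 | 50 | 50/51 = 98% |

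A range of 17% to 98% shows that the share cannot be determined from the documents. It is not an estimate.

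**Baseline effect on mean CK change (all values assumed).** Let f be the share of patients with an acute-phase baseline CK0 that falls to 100 U/L, with all others rising by 15 U/L:

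mean change = (1 − f) × 15 + f × (100 − CK0)

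This is zero when f/(1 − f) = 15/(CK0 − 100).

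- CK0 = 800: 15/700 = 0.0214, so f = 2.1%.
- CK0 = 1500: 15/1400 = 0.0107, so f = 1.1%.

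Check at f = 2%: CK0 = 800 gives 14.7 − 14.0 = +0.7 U/L, and CK0 = 1500 gives 14.7 − 28.0 = −13.3 U/L.

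Of 10,000 patients, 1.1-2.1% is about 110-210. The inpatient limit allows 0.20 × 10,000 = 2,000, so the crossing point lies at roughly 5-10% of the permitted inpatients.

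**The median in the same illustration.** Every patient without an acute baseline changes by +15, so the median change is +15 for any f below 50%. Individual spread would move it somewhat, but far less than the mean.

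**AST (assumed).** Shift in mean = −f × excess. With f of 1-20% and an excess of 0.5-2 × ULN, it runs from −0.01 × 0.5 = −0.005 to −0.20 × 2 = −0.4 × ULN.

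**The case against.** A reader might infer that the study's muscle and liver signals are contaminated throughout, and that a real CK rise in other patients would be hidden. The documents do not support that:

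- ACS is very high risk by definition, so the low, moderate and high rows contain no patients with ACS at baseline. A rise in those patients stays visible.
- SAP 8.1 requires the median, minimum and maximum alongside the mean.
- The persistent ALT/AST endpoint needs two successive values above three times ULN, 4 to 10 days apart. This largely protects it from a brief infarct-related AST rise. The AST point is confined to mean change and the plain percentage abnormal.
- Post-baseline samples come at Week 12 and at unplanned visits from Week 4. An infarct CK peak enters only if it is recorded at such a visit or as an adverse event.
- The baseline window reaches back one month, so not every ACS baseline is an acute value. A large acute share is also unlikely: 15% would be 1,500 patients, or 75% of the 2,000 inpatients allowed, if they all came from the ward.
- Special-interest events are tabulated by preferred term, so a CK-increase term would stand apart from myalgia or rhabdomyolysis.
- Safety is a secondary objective, and the SAP has no hypotheses or decision rules.

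All of this stands, and it narrows the point. It does not remove the double counting, or the effect on the mean in the overall and very-high rows.

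A second tempting step is to drop cardiac-adjacent CK values from the headline count. That would depart from the protocol's own muscle criterion and would be the less conservative choice for safety reporting.

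**Conclusion.** The point holds in a limited form. A CK of 10 times ULN recorded around an MI, PCI or CABG would count both as a muscle event and alongside a cardiovascular event, and nothing in the SAP would show the overlap. Acute-phase baselines can pull down the mean CK and AST change in the overall row and the very-high-risk stratum. The low, moderate and high strata, the medians and the persistent ALT/AST endpoint are largely unaffected for change from baseline.

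The size cannot be determined from the documents. The crossing point of about 1-2% of patients rests on three assumptions: a baseline CK of 800-1500 U/L, a fall to 100 U/L, and a uniform 15 U/L rise in all others. It shows that a small group can dominate a mean. It does not show that the sign will reverse in this study. The point is worth acting on because the remedy is cheap. The primary endpoint is not affected.

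**What to change.** Keep the protocol-defined count of CK at 10 times ULN as the headline, and add to SAP 6.2 and 8.2:

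1. The same count excluding post-baseline values within a pre-specified interval of an MI, PCI or CABG event. List the excluded values beside the event. Fix the interval before data lock.
2. CK and AST change from baseline split by ACS at baseline (yes/no), including by dose within the very-high stratum.
3. A baseline-to-Week-12 shift table for CK and AST in multiples of ULN. State that CK/AST change will be interpreted from the non-ACS rows and this table.

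The cost is SAP wording and a few extra tables, with smaller cells in the split rows. No new data are needed: ACS status is already required for risk stratification, and the events and laboratory values are collected. No safety event is removed from the report.

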Primary Endpoint	
 
• Achievement rate of Low Density Lipoprotein-Cholesterol (LDL-C) goals at 12 weeks of therapy of Atorvastatin according to Chinese Guideline on Dyslipidemia Prevention and Treatment in Adult (2007 version). It will be presented with the proportion of patients who achieve the LDL-C goal value with the corresponding 95% confidence interval. (Please find the detailed description in the section 8.1.2) 
 
■ The time of 12-week will be calculated from the day when patient start taking atorvastatin.
 
 
 

Secondary Endpoints	
 
• Dosage distribution of Atorvastatin in cardiology patients with different risk categories at the end of 12-week follow-up
 
• Safety and tolerability will be evaluated by recording the incidence and severity of adverse events, abnormal physical examination findings, and abnormal laboratory values through 12 weeks of treatment. Especially monitoring the proportion of patients who have any following events: 
 
■ Muscle symptoms such as myalgia, fatigue, weakness, creatine kinase values 10 times the upper limit of normal, and rhabdomyolysis
 
■ Persistent elevations in Alanine Aminotransferase/ Aspartate Aminotransferase (ALT/AST) > 3 Upper Limit of Normal (ULN).
 
■ Major adverse cardiovascular events
 
 
 
• Dropouts percentage and reason through 12 weeks of follow-up;
 

Observation Duration	12 weeks
Statistics	Sample size consideration: 
 
• The non-interventional (NI) study is designed to detect the
 

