#### 8.1.2. Study Endpoint

- **Primary endpoint**

- Achievement rate of LDL-C goals at 12 weeks of therapy of Atorvastatin according to Chinese Guideline on Dyslipidemia Prevention and Treatment in Adult (2007 version). It will be presented with the proportion of patients who achieve the LDL-C goal value. LDL-C target value for the patients with different risk level is defined in the [section 8.2.5](#) per guideline.

$$\text{Achievement Rate} = \frac{\text{No. subjects who achieve LDL-C target value}}{\text{No. subjects who complete 12-week follow up}}$$

- The time of 12-week will be calculated from the day when each patient starts taking atorvastatin. .
- Achievement rate will be summarized overall, within each risk strata, and by dose within each risk strata. 95% confidence intervals will be provided.

- **Secondary endpoint**

- Dosage distribution of Atorvastatin in cardiology patients with different risk stratification at the end of 12-week follow-up
- Safety and tolerability will be evaluated by recording the incidence and severity of adverse events, abnormal physical examination findings, and abnormal laboratory values through 12 weeks of treatment. Especially monitoring the patients who have any the following events:
  - Having muscle symptoms such as myalgia, fatigue, weakness, creatine kinase values 10 times the upper limit of normal, or rhabdomyolysis,
  - Having persistent elevation in alanine aminotransferase, aspartate aminotransferase, or both (defined as two consecutive measurements obtained 4 to 10 days apart that is more than three times the upper limit of the normal range).

- Major adverse cardiovascular events will also be recorded as adverse events, including death, myocardial infarction, stroke, documented unstable angina requiring re-hospitalization, revascularization with either percutaneous coronary intervention or coronary-artery bypass grafting.

Adverse events will be summarized overall and by dose within each risk strata.

- Dropout percentage and reason through 12 weeks of follow-up;

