### 8.3. Variables

This study will collect and analyze the effectiveness and safety data from approximately 10,000 eligible subjects from the time of first subject first visit to the time the study is closed. Since this is primarily an observational study, patient subsequent visits are set according to the return dates in clinical practice, which are supposed to be week 12 and any unplanned visits during week 4 to week 16.

- Demographic information includes patients' birth date, gender, body height and weight;
- Medical history includes information on current medical history, previous medical history, family history of premature cardiovascular disease and history of smoking ;
- Laboratory examination includes liver function [ ALT, AST, total bilirubin (TBil)], serum lipid parameter (LDL-C, HDL-C, TG, Total-C), creatine kinase value (CK) and renal function [creatinine (Cr), blood urea nitrogen (BUN), uric acid (UA)];
- Major adverse cardiovascular events including death, myocardial infarction, stroke, documented unstable angina requiring re-hospitalization, revascularization with either percutaneous coronary intervention or coronary-artery bypass grafting
- Other adverse events. (Details in [Section 10](#) MANAGEMENT AND REPORTING OF ADVERSE EVENTS/ADVERSE REACTIONS)
- Medication record: dosage and duration of Atorvastatin, as well as any dose change including reasons will be recorded.
- Concomitant drugs: antiplatelet drugs, angiotensin converting enzyme inhibitors (ACEI)/ angiotensin receptor blockers (ARB),  $\beta$ -block, diuretics and calcium antagonist are concomitantly used or not.

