8.2 STATISTICAL ANALYSES

- **Analysis of Primary (Efficacy) Endpoint**

The primary (efficacy) analysis will be conducted in the FAS analysis population. The proportion of Achievement rate for LDL-C at Week 12 defined as the primary endpoint will be analyzed by calculating a point estimate with confidence interval (CI).

Achievement rate for LDL-C will be summarized overall, within each CVD risk strata, and by dose group within each CVD risk strata. 95% confidence intervals will be estimated.

In addition, percentage of patients who achieve LDL-C therapy target will also be tabulated by sex, age group, dose group and baseline disease type.

- **Secondary Endpoints and Safety Analyses**

Analysis of lipid values and change and percent change in lipid values at week 12 will be performed on the FAS populations. Analysis of the remaining secondary endpoints and safety data will be done on SAS (See [Section 5.2](#)). Data summaries will be presented in tabular and/or and summarized descriptively, where appropriate.

Lipid Parameters

Descriptive summary will be tabulated overall and by dose group within each CVD risk level for percent (%) change from baseline for TC, HDL-C and LDL-C and TG at Week 12.

Study Drug Exposure

Exposure to atorvastatin will be summarized descriptively overall, and by CVD risk level. Duration (days) of study drug taken, daily dose, dose at week 12, and total dose will be summarized. Listings of dosing records with the reason of change dose will also be provided.

Adverse Events

Adverse events will be classified using the medical dictionary for regulatory activities (MedDRA) classification system. The severity of adverse events will be graded according to the principal investigatory judgment and collected in CRF.

Adverse events (such as treatment emergent adverse events; treatment-related adverse events; and serious adverse events, adverse event from early termination to final visit, will be summarized by system organ class (SOC) and preferred term (PT) according to MedDRA terminology.

Adverse events will be summarized overall and by dose group within each CVD risk strata by SOC and preferred term.

Adverse events of special interest ([section 6.2](#)) will be tabulated by preferred term (PT) overall and by dose group within each CVD risk level.

Adverse events leading to discontinuation of trial treatment will be presented overall and by dose group within each CDV risk level.

Dropouts

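### The SAP separates death from the protocol's MACE composite without explanation and specifies no once-per-patient MACE proportion

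*SAP*

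**What the plan says.** The protocol defines the composite twice, with death as the first component each time. Section 8.1.2 (Study Endpoint) has "Major adverse cardiovascular events will also be recorded as adverse events, including death, myocardial infarction, stroke, documented unstable angina requiring re-hospitalization", and section 8.3 (Variables) has "Major adverse cardiovascular events including death, myocardial infarction, stroke, documented unstable angina requiring re-hospitalization". Both go on to coronary revascularisation.

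The summary measure is in the abstract (section 3), under the secondary endpoints: "Especially monitoring the proportion of patients who have any following events". MACE is one of the three items listed below that line.

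SAP 6.2 introduces its groups with "The Adverse Events Special Interest (AESI) will be categorized as below". The cardiovascular group begins "Major cardiovascular events: myocardial infarction, stroke, unstable angina requiring re-hospitalization" and closes with coronary revascularisation. Death is the next bullet, as a category of its own.

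SAP 8.2 says how these events are shown: they "will be tabulated by preferred term (PT) overall and by dose group within each CVD risk level". Neither this section nor any other part of the SAP specifies a count of patients with at least one event in the cardiovascular group, with or without death.

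**The concern.** The protocol singles out MACE for special monitoring and, in the abstract, asks for a patient-level proportion. The SAP changes the composition of the event group and specifies a different unit of tabulation. Two things follow.

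- **Definition.** A programmer who adds a category total from SAP 6.2 would produce a composite without death. Its name is close to the protocol's term, and a reader could take the two as equivalent.
- **Counting.** With preferred-term rows alone, the report would not let a reader recover the protocol's proportion. One patient may have an infarction, a revascularisation and then die, and the table does not show that overlap.

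Safety is a stated secondary objective. The population includes acute coronary syndromes (the very-high-risk stratum in protocol 8.2.5) and up to 20% ward inpatients (protocol 8.2.2), so some deaths within 12 weeks are plausible. If the composite is not fixed in advance, its definition may be settled after the events have been seen.

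**Working it through.** **1. The plan's own figures.** Neither document states a MACE rate, count or proportion, so there is nothing on this endpoint to reproduce. The only planning figure is the sample size for the LDL-C achievement rate: n = 1.96² × 0.60 × 0.40 / 0.011² = 7620 against the stated 7600, and 7600 / (1 − 0.24) = 10,000. It reproduces, and it has no bearing on this point except to suggest about 10,000 treated patients.

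**2. The definitions side by side.**

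| Element | Protocol 8.1.2 and 8.3 | SAP 6.2 |
|---|---|---|
| Death | inside MACE | separate category |
| Myocardial infarction | inside | inside |
| Stroke | inside | inside |
| Unstable angina with re-hospitalisation | inside, must be documented | inside, that qualifier absent |
| Revascularisation (PCI or CABG) | inside | inside |
| Unit of summary | proportion of patients (abstract) | preferred-term rows (SAP 8.2) |

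The SAP does not limit infarction or stroke to non-fatal events. A fatal infarction or stroke recorded as such is therefore in its cardiovascular group. Only patients who die with no listed component fall outside it.

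**3. Was the split announced?** SAP section 1 lists one change, the widening of the Week 12 window. No reason for moving death appears there or elsewhere.

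**4. Can the composite be rebuilt from the planned rows?** No. Illustrative counts: 100 patients with infarction, 120 with revascularisation, 80 with both.

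- Sum of rows: 100 + 120 = 220
- Distinct patients: 100 + 120 − 80 = 140
- Overcount: 220 / 140 − 1 = 57%

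A separate death row does not settle the matter, because its overlap with the other rows is not shown.

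**5. How far could a total of the SAP category differ from the protocol's composite?** Let C be the proportion of treated patients with at least one listed component, and D the proportion who die with none.

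- SAP category, if totalled once per patient: C
- Protocol composite: C + D
- Relative shortfall: D / (C + D)

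The documents give neither C nor D. The values below are assumptions, with 10,000 treated patients.

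| D | Patients | Composite at C = 1.0% | Shortfall | Composite at C = 2.0% | Shortfall |
|---|---|---|---|---|---|
| 0% | 0 | 1.0% | 0% | 2.0% | 0% |
| 0.1% | 10 | 1.1% | 9% | 2.1% | 5% |
| 0.3% | 30 | 1.3% | 23% | 2.3% | 13% |
| 0.5% | 50 | 1.5% | 33% | 2.5% | 20% |

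Steps 4 and 5 pull in opposite directions. Adding rows can overstate the number of patients, while totalling the SAP category can understate the composite. The direction of error in a reader's reconstruction is not fixed.

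**The case against.** The other side has several good points.

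- **Deaths are not lost.** Death is its own category of special interest, so it is tabulated overall and by dose group within risk level. A fatal event is also a serious adverse event under protocol section 10, and SAP 8.2 summarises those. This stands: what is missing is the combined row, not the mortality data.
- **The SAP is allowed to differ.** Protocol 8.7 lets the SAP modify the protocol's plans and requires an amendment only for major changes to the primary endpoint or its analysis. This makes the change permissible. It does not show that the change was intended, and the SAP's change log does not mention it.
- **The patient proportion is spelled out only in the abstract.** Protocol 8.1.2 speaks of monitoring patients with these events and of summarising adverse events by dose within risk strata. That weakens the requirement somewhat. Still, the abstract is part of the protocol, and nothing in the body contradicts it.
- **Table shells could add a total.** SAP section 9 leaves the shells to the analysis team, so one cannot say that the proportion will never be produced, only that it is not specified. A shell built on the SAP 6.2 definition would still leave death out of the total.

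A reader might go further and infer that the SAP's MACE figure is too low. The documents do not support that. The SAP specifies no MACE total that could be low. If a total were made, it would be low only if at least one patient died without another listed component, and no event rate is given.

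**Conclusion.** The mismatch is in the text. The protocol puts death inside MACE and its abstract asks for a proportion of patients. The SAP moves death to a separate category without explanation and specifies preferred-term rows only. The protocol's once-per-patient MACE proportion is therefore not specified and could not be derived from the tables as described.

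The numerical effect is unknown. On the assumed rates in the working, a total of the SAP category would fall short of the protocol's composite by 0% to 33% at a 1.0% component rate, and by 0% to 20% at 2.0%. The zero end applies if every patient who dies also has a listed component.

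The weight of the point is limited. This is a descriptive secondary safety endpoint, there are no formal hypotheses, and the LDL-C analysis is untouched. It should still be corrected, because MACE is one of only three event groups the protocol singles out and the correction is nearly free.

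**What to change.** - **SAP 6.2:** define the category as in protocol 8.1.2 and 8.3, with death as a component and the same wording for the others. If a category without death is also wanted, give it a distinct name and state the reason.
- **SAP 8.2:** add one row with the number and percentage of safety-set patients with at least one protocol-defined MACE, each patient counted once, overall and by dose group within CVD risk level. Keep the component and death rows.
- **Timing:** make the change before data lock and record it in SAP section 1.

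The cost is an edited definition and one extra table row. Protocol 8.3 already lists MACE, death included, among the variables to be collected, so no new data or method is needed. The reported MACE proportion may be somewhat higher than a total that leaves death out.
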